All biopsy specimens should be labeled with the date of collection and the unique identifier (called the Lab ID#), which the site will assign to each participant. We are not labeling the actual specimens with the WIHS ID because we are using such small cryovials and the receiving lab here in San Francisco requested we use a system that allows all the information to be on the tube directly.

Every specimen shipping form will have both the WIHSID # and the Lab ID#. The Lab code always starts with W (for WIHS), then a number from 1-6, denoting the WIHS Site (1=Bronx; 2=Brooklyn; 3=Washington, D.C.; 4=Los Angeles; 5=San Francisco; 6=Chicago). The last number is assigned sequentially as participants are enrolled. First participant at your site =1, second =2, etc.

Each specimen will be labeled with a 5-digit alphanumeric code that contains the Lab ID# and a code for the type of specimen. The code is explained below. For example, W51-EP would be assigned for endometrium preserved in formalin for the first participant enrolled at the San Francisco WIHS site. W52-IF would be assigned for a frozen ileal specimen from the second San Francisco WIHS participant enrolled.

W= WIHS

[S]= indicates which WIHS Site nationally (will be a number from 1-6)

[N]= Unique to participant, assigned in the order in which participants at each site are enrolled. First participant = 1, second = 2, etc.

Next letter= Specimen type

S = Sigmoid colon

I = Ileum

P = Cervical sPonge (Merocel spear)

W=Cervical Wick for HIV VL (TearFlo strip)

E = Endometrium

Y = Endocervical cYtobrush (San Francisco only)

C = Cervical transformation zone

B = Blood

Last Letter= How specimen received in Lab

F = Frozen

P = Formalin (Preserved)

C = Fresh (Cells) (San Francisco only)

SPECIMENS IN ORDER OF COLLECTION	Frozen Specimens	Fresh Specimens (SAN FRANCISCO ONLY)	Specimens in Formalin
Ileal biopsy	W __ -IF	W __ -IC	W __ -IP (2 containers: one with 4-5 pieces, one with 1 piece)
Sigmoid colon biopsy	W __ SF	W __ -SC	W __ -SP (2 containers: one with 4-5 pieces, one with 1 piece)
Cervical sponge for cytokines	W __ -PF	W __ -PC	N/A
Cervical wick in lysis buffer for HIV VL (HIV + participants only)	W __ -WF	N/A	N/A
Endocervical cytobrush *	N/A	W __ -YC	N/A
Endometrial biopsy	W __ -EF	W __ -EC	W __ -EP
Cervical transformation zone biopsy	W __ -CF	W __ -CC	W __ -CP
Blood for PBMCs*	N/A	W __ -BC	N/A
Plasma for HIV VL (HIV + participants only)	W __ -BF	N/A	N/A

2. **SHIPPING SPECIMENS:**

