2. STUDY PROCEDURES

a. Pre-eligibility:

WIHS sites will be provided with lists of potentially eligible participants based on the Inclusion and Exclusion Criteria listed below. Study staff will then approach potentially eligible participants at their next regularly scheduled Core Visit. Participants who are interested will have a Pre-Eligibility Screening Interview at the end of the Core Visit. Those who appear eligible will be scheduled for a Screening Visit. (*See Appendix C: Time and Events Schedule.*)

b. Screening Visit

The Screening Visit will be scheduled as soon as possible after the WIHS Core Visit. Informed consent will be obtained at this visit. All participants will answer questions about medical history, current medications, and use of intravaginal products. Urine testing for pregnancy will be performed. Participants with a positive pregnancy test will not continue in the study. Blood will be drawn for prothrombin and partial

thromboplastin tests (PT and PTT). HIV-positive participants will have blood drawn for HIV viral load, since it is anticipated that results from the prior WIHS Core Visit will not yet be available. HIV-positive participants will also be asked to report any acute medical illnesses occurring during the study period and to avoid vaccinations during the study if this can be done without compromising their health. These measures are requested because of the potential for HIV viral load changes associated with acute medical illness and vaccination.

Participants will be instructed how to perform at-home urine testing to detect luteinizing hormone (LH). LH peaks just before ovulation, and is detectable in the urine in the early luteal phase.

Study staff will dispense Clearblue brand LH surge kits (Proctor & Gamble, Cincinnati, OH) and assist the participant in determining when to start testing. (*See Appendix D: When to Start LH Surge Testing.*) The participant will notify site staff when LH is detected in the urine, so that the Endometrial Biopsy Visit can be scheduled within 7 to 9 days, at which time the participant will be in the mid-to-late luteal phase. Participants will be encouraged to contact site staff should *any* questions or concerns arise during urine testing. Study staff may also contact participants.

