home (for example, those marginally housed or living in places where bathroom access is limited), one option is to offer hospitalization at a local research center overnight. Sites should also consider this option for participants with very difficult peripheral venous access, for whom placement of a peripherally inserted central catheter (PICC) line is necessary. Sites with access to CTSA-funded CRCs may consider applying for overnight admission visits for participants who have difficulty traveling to study visits, or who are anticipated to have difficulty with the Bowel Prep.

d. *Biopsy Visit:*

FOR SOME SITES, IT WILL NOT BE POSSIBLE TO SCHEDULE THE COLONOSCOPY AND ENDOMETRIAL BIOPSY ON THE SAME DAY. IN THAT CASE, THE ENDOMETRIAL BIOPSY SHOULD STILL BE SCHEDULED BASED ON THE LH SURGE. THE COLONOSCOPY CAN BE SCHEDULED WITHIN 7 DAYS ON EITHER SIDE OF THE ENDOMETRIAL BIOPSY.

SITES PERFORMING GYNECOLOGICAL SPECIMEN COLLECTION WITHOUT SEDATION MAY WANT TO CONSIDER OFFERING PARTICIPANTS IBUPROFEN AND/OR PARACERVICAL BLOCK.

This visit will occur 7 to 9 days after the LH surge is detected, during the mid-to-late luteal phase of the menstrual cycle, when the depth of endometrial tissue is greatest. Participants will undergo a colonoscopy and endometrial biopsy (EMB). Immediately prior to these procedures, we will conduct a brief interview to collect health history and information on medication use and recent intravaginal product use. A urine sample will be collected to rule out pregnancy. Participants with a positive pregnancy test or recent intravaginal product use will not continue in the study.

Continuing participants will be assessed by the site colonoscopist who will determine the appropriate intravenous (IV) sedation to administer. Participants will have an IV line placed by Endoscopy Nursing staff. Before sedation is administered, blood for serum progesterone will be drawn through the IV line. Serum progesterone levels will be run locally to confirm menstrual cycle phase in case the histologic dating of the endometrium is equivocal. If colonoscopy and endometrial biopsy are being performed at separate visits, serum progesterone should be drawn at the EMB visit.

For HIV-positive participants, one 5-6 ml lavender top EDTA tube should be drawn at the same time as the serum progesterone. This will be used to compare HIV viral load in plasma to that in cervical secretions.

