The participant will be sent to the recovery area, where she will be monitored for approximately 2 to 3 hours, until sedation wears off. Because of safety concerns after sedation, the participant will be advised not to drive or operate heavy machinery for 24 hours after the procedures. It is conventional for Endoscopy staff to refuse to discharge a patient who has received sedation without a responsible adult to accompany her home. The SC will arrange transportation via a medical cab service for participants who do not have a responsible adult to accompany them. Regardless of participant's transportation home, SC will be present at discharge. Furthermore, some Endoscopy staff may also require that the provider who performed the EMB clear the participant for discharge (i.e., confirm that there are no complications from the EMB), in addition to the clearance given by the colonoscopist.

The participant will be given post-procedure instructions. The SC will also contact the participant that evening, the next day, and again one and two weeks later to be sure she is not experiencing any adverse events.

3. INCLUSION CRITERIA:

1. WIHS participants between 18 and 44 years of age.
2. Regular menstrual cycles (21 to 35 days).
3. HIV-negative women *OR* women who meet the criteria for the HIV disease progression groups listed above. All positive participants must have documented HIV positivity for at least three years. (*See Appendix B for detailed definitions of the eligibility groups.*)
4. Participant must be willing and able to perform urine testing at home and to report for an Endometrial Biopsy Visit 7 to 9 days after testing confirms that LH surge has occurred, with Colonoscopy Visit occurring the same day or within seven days.
5. Participant must be willing and able to refrain from using vaginal products for 10 days prior to the Endometrial Biopsy Visit.
6. Participant must be willing and able to refrain from vaginal intercourse or to use nonlubricated condoms for 72 hours prior to the Endometrial Biopsy Visit.
7. Participant must be willing and able to perform Bowel Prep.

4. EXCLUSION CRITERIA:

1. History of hysterectomy.
2. Allergies to latex or iodine.
3. History of bleeding dyscrasias; current anticoagulant therapy or abnormal screening coagulation studies.
4. History of inflammatory bowel disease.
5. Currently breastfeeding, pregnant, or planning a pregnancy in the near future. Has breastfed in the last six months.

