6. Current or recent abnormal vaginal discharge and/or abnormal vaginal bleeding.
7. Current genital herpes outbreak, and/or greater than four outbreaks/year. (Suppressive therapy for genital herpes is **NOT** exclusionary.)
8. Any active uterine or gut infection.
9. Recent (within 14 days of Biopsy Visit) upper respiratory infection, urinary tract infection, vaginitis, systemic illness with fever or diarrhea, or vaccination.
10. Abnormal Pap smear in the last 12 months.
11. Use of intrauterine device in the last 12 months.
12. Use of hormonal contraceptives or sex hormones within the last 12 months.

13. Use of supraphysiologic levels of glucocorticoid therapy or other potential immunomodulatory therapy within the past 30 days. (Use of inhaled steroids for asthma is **NOT** exclusionary.)
14. Other conditions that, in the opinion of the investigator, would compromise the participant's ability to comply with the study protocol, such as a major psychiatric disorder, or inebriation or cognitive impairment sufficient to interfere with participant's ability to give informed consent.

D. COMPENSATION

Participants will be reimbursed for the Screening Visit and for the Biopsy Visit(s) at the discretion of each site. For example, SF is reimbursing \$25 for screening and \$125 for the Biopsy Visit. Participants whose Bowel Prep is deemed inadequate to perform colonoscopy will be reimbursed \$20. The participant will be offered re-enrollment with her next menstrual cycle at the discretion of the site's Principal Investigator and the Study Coordinator.

E. SPECIMEN DISPOSITION

1. LABELING SPECIMENS:

San Francisco will supply Merocel sponges, Wheaton cryovials and cryo-labels to all the sites. They will also supply preprinted labels for the formalin containers. Sites will supply their own formalin containers. A layer of blank packing tape should be placed over the formalin container label to prevent running of the ink should containers come in contact with liquids.

San Francisco will supply cryo-labels and Corning cryovials with lysis buffer (orange cap) for collection of cervical secretions in HIV-positive participants, and cryo-labels and cryovials for collection of plasma for HIV viral load. Sites will supply their own EDTA blood collection tubes.

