34 days	Day 17
35 days	Day 18

TEST PROCEDURE

Instruct the participant:

1. You may test your urine at any time of the day; however, you should try to do it the same time of the day every day. Most people find it easiest to do first thing in the morning.

Also, reduce your liquid intake and try not to urinate for about four hours before testing, since a diluted urine sample can hinder LH detection.

2. To begin testing, open the sealed pouch and remove the test stick from the pouch. Remove the white cap. This will expose the absorbent strip.
3. Point the absorbent strip downward. Place it in your urine stream for about five seconds so that it gets thoroughly wet. Try not to get any urine on the results window.
4. When you take the stick out of your urine stream, keep holding it with the absorbent strip down. You do not have to recap the stick, but can if you want to.
5. Lay the stick flat on a table, and wait for colored lines to appear. You can read the results anytime between three and ten minutes after using the test.

INTERPRETATION OF RESULTS

Negative - No LH Surge: Only one colored line appears **OR** the surge line (closest to the arrow) band is much lighter than the reference line. There is no LH surge. Test again tomorrow.

Positive - LH Surge: If two colored lines are visible and the surge line (the line closest to the arrow) is equal to or darker than the reference line, you are about to ovulate. ***Call us to schedule your Biopsy Visit!***

Invalid: No visible line at all. The reference line will not appear if not enough urine hit the absorbent tip. Repeat with a new test kit. Please reread the instructions and follow them precisely. The most common reason for an invalid test result is that urine has splashed into the interpretation window. This prevents liquid from properly “wicking” up the test and through the band of dye. Please note that invalid results can nearly always be avoided by placing your thumb over the interpretation window while holding the test in the urine stream.

FREQUENTLY ASKED QUESTIONS

1. *Should I restrict my diet before taking the test?*
No, diet will not affect the test results.
2. *Today's reference line is a different shade of blue than yesterdays. Is this a concern?*

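### The biopsy-day urine test cannot verify that a participant has not conceived in the biopsy cycle, and no visible precaution covers the days around ovulation

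*Protocol*

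**What the plan says.** **Pregnancy.** Exclusion criterion 5 (Protocol C.4) covers women "Currently breastfeeding, pregnant, or planning a pregnancy in the near future". At screening (C.2.b), "Urine testing for pregnancy will be performed". At the biopsy visit (C.2.d), "A urine sample will be collected to rule out pregnancy". A positive result at either visit ends participation.

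**Timing.** Section C.2.d fixes the biopsy: "This visit will occur 7 to 9 days after the LH surge is detected, during the mid-to-late luteal phase of the menstrual cycle". On what the LH test marks, C.2.b says "LH peaks just before ovulation, and is detectable in the urine in the early luteal phase". Appendix D tells a participant that if the surge line "is equal to or darker than the reference line, you are about to ovulate".

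**Intercourse.** Inclusion criterion 6 (C.3) requires willingness to "refrain from vaginal intercourse or to use nonlubricated condoms for 72 hours prior to the Endometrial Biopsy Visit". C.2.b supplies condoms for those same 72 hours, and the Appendix E reminder refers to at least 3 days.

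**Contraception.** Exclusion criterion 12 is "Use of hormonal contraceptives or sex hormones within the last 12 months", and criterion 11 excludes IUD use over the same period. Appendix E has a one-line prompt on birth control for the first contact with a participant. It attaches no requirement to the answer.

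**The concern.** The sponsor clearly intends that no pregnant woman has the biopsy: there is an exclusion, a test at two visits and a stop rule. But the biopsy is deliberately placed about a week after ovulation. A conception in that cycle would be only days old, and the screening test, done before home LH testing begins, could not have seen it. The women eligible are 18 to 44 years old, cycle regularly and have not used an IUD or hormonal method for a year.

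At stake is participant safety. The endometrial sampling is a suction procedure done for research, and a negative urine result that day could reassure falsely. A second, weaker consequence is possible. The background section (B.2) names tolerance of an embryo and uterine NK cells as distinctive features of endometrium, so tissue from a conception cycle might differ for reasons unrelated to HIV. The protocol offers nothing to show that it would differ this early, so this is only a possibility.

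**Working it through.** The protocol states no figure to reproduce. The check is a day count, with LH detection as day 0.

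**Inputs from the protocol**
- Biopsy and biopsy-day urine test: day b = 7, 8 or 9 (C.2.d).
- Intercourse restriction: the 3 days before biopsy (C.3, criterion 6).
- Ovulation: shortly after LH detection (C.2.b, Appendix D), with no number of days given.
- First day of home LH testing: Appendix D chart, equal to cycle length minus 17 for cycles of 22 to 35 days and minus 16 for 21 days.

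**Assumptions, not in the protocol**
- Ovulation on day o = 0, 1 or 2.
- Luteal phase of l = 12 to 16 days.

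**Step 1. Start of the restriction:** b − 3.
- 7 − 3 = 4 and 9 − 3 = 6, so it starts on day 4 to 6.

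**Step 2. Gap from ovulation to the restriction:** b − 3 − o.
- Smallest: 7 − 3 − 2 = 2 days. Largest: 9 − 3 − 0 = 6 days.
- The restriction never reaches back to ovulation or the days before it.

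**Step 3. Age of the cycle at the test:** b − o.
- Smallest: 7 − 2 = 5 days after ovulation. Largest: 9 − 0 = 9 days.

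**Step 4. Days from the test to expected menses:** o + l − b.
- Smallest: 0 + 12 − 9 = 3. Largest: 2 + 16 − 7 = 11.
- Central case (o = 1, l = 14): 15 − 9 = 6 to 15 − 7 = 8.

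**Step 5. Cross-check from the Appendix D chart, without a luteal length.** For cycle length L, first test day d and surge on test day k, the biopsy is on cycle day d + k − 1 + b and menses are expected on day L + 1. The interval is (L − d) + 2 − k − b.
- k = 4: from 16 + 2 − 4 − 9 = 5 to 17 + 2 − 4 − 7 = 8 days.
- k = 1 to 6 (assumed range): from 16 + 2 − 6 − 9 = 3 to 17 + 2 − 1 − 7 = 11 days, the same range as Step 4.

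**Step 6. A literal reading of C.2.b.** Its phrase about the early luteal phase could mean that urine detection follows ovulation. Taking o = −1, the gap in Step 2 lengthens to at most 9 − 3 + 1 = 7 days, and the smallest interval in Step 4 becomes −1 + 12 − 9 = 2 days. The conclusion is unchanged.

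**Step 7. Other checks in the schedule.**
- The biopsy-day interview (C.2.d) covers health history, medication and intravaginal products. Intercourse is not listed.
- Serum progesterone is drawn to confirm cycle phase.
- When the visits are split, Appendix E repeats the urine test at colonoscopy, which may be up to 7 days after the biopsy: day 7 + 7 = 14 to 9 + 7 = 16. A conception could first show then, after the endometrium has been sampled.

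**The case against.** **The exclusion can be met.** A reader might infer that no woman could satisfy exclusion 5. That goes too far. Women who are abstinent, sterilised or consistent condom users satisfy it, and none of these is barred. What fails is verification for a conception in the current cycle.

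**The 72-hour rule is not a failed contraceptive measure.** A reader might also infer that inclusion 6 contradicts exclusion 5. The protocol never presents the rule as contraception. It specifies nonlubricated condoms and stands beside the rule on vaginal products, which points to specimen protection. This objection stands: the rule may serve its own purpose well. The gap is that nothing else visible covers ovulation.

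**Other text may fill the gap.** Women planning a pregnancy are excluded, and Appendix E prompts on birth control. The first addresses intent, not unplanned conception; the second is a prompt. The consent pages were removed and the interview forms are not shown, so advice there cannot be ruled out. Even so, the criteria, the condom-dispensing text and the Appendix E reminder all stop at about three days.

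**Test performance is not given.** This is true. The protocol names no pregnancy assay and no sensitivity. Equally, it gives no basis for relying on a urine result 5 to 9 days after ovulation.

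**Conclusion.** The point holds as a participant-safety flaw in the schedule. Followed exactly, the visible protocol allows a woman who may have conceived in the biopsy cycle to have a research suction biopsy after a negative test.

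Its size is expressed in days: the restriction begins 2 to 6 days after ovulation, and the test falls 3 to 11 days before expected menses. Both ranges rest on the assumed ovulation lag and, for the second, on luteal length; the ordering holds throughout. The conclusion also assumes that a urine test cannot be relied on before a missed period.

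A reader may want the number of women affected among the planned 50. The protocol gives no frequency of intercourse, contraceptive use or conception, so no count is supported. Nor does it support a claim that the immune readouts would be biased.

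**What to change.** Reconcile exclusion criterion 5, inclusion criterion 6, the LH-based visit timing and the statement in C.2.d about the purpose of the urine test, so that the pregnancy precaution the sponsor chooses covers the ovulation of the biopsy cycle. Which precaution that should be is for the sponsor to decide.

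Then:
- Carry the chosen precaution into the condom-dispensing text in C.2.b, the Appendix C schedule and the Appendix E reminders.
- Stop relying on the biopsy-day urine test alone to exclude pregnancy.
- Have the existing biopsy-day interview ask about possible conception in the current cycle.
- If the consent form or interview forms already deal with this, bring the protocol into line with them.

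The cost is an amendment to a few passages and one added interview topic; condoms are already dispensed at screening. The drawback is a longer precaution for participants, and some may decline to take part.

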APPENDIX A: COMPARISON OF GALT TO ENDOMETRIUM

Comparator	Endometrium	GALT
Barrier function	Frequent entry of lower genital tract constituents (Barnhart 2001; Dayal 2003)	Intense bacterial colonization
Induction of immune tolerance	Distinguishes foreign embryo from pathogens (Doukhouhaki 2006)	Distinguishes desirable flora from pathogens
Variation in cell types	Cellular constituents vary over ovulatory cycle	Cellular constituents vary with anatomic location
Lymphoid aggregates	Cycle variable B cells surrounded by CD8/45 RO+ T cells, and an outer halo of CD14+ monocytes/macrophages present at the stratum basalis, and NK aggregates at endothelial layers (Sentman 2004)	Peyers patches, M cells, isolated follicles
Microvillus epithelium	Post-luteal epithelium	Small bowel
Antigen presentation	Epithelial cells (Fahey 2006)	Epithelial cells
Origin of lymphoid cells	Most traffic in (Yeaman 2001)	Most traffic in
T cell type	CD8+ T cells predominate	CD8+ T cells predominate
$\gamma\delta$ -T cells	$\gamma\delta$ -T cells represent approximately 10% of intraepithelial T cells	$\gamma\delta$ -T cells represent approximately 10% of intraepithelial T cells
Defensins	α - and β -defensins are present depending on inflammation, infection, and cycle phase	α - and β --defensins are present depending on inflammation and infection
Sex steroid responsive	Significant modulation of cell types, apoptosis, tissue anatomy	Estrogen receptor ligands affect IBD, estrogen inhibit gut NK- κ B transcription (Kayisli)

APPENDIX B: DEFINITIONS OF PHENOTYPE GROUPS FOR POSITIVE WOMEN

Women in all categories must have been HIV positive for at least three years, plus:

Natural Controllers
	
 • HIV viral load consistently below the WIHS level of detectability. • Never used HAART or HAART use during pregnancy only.

Good CD4 Responders to HAART
	
 • CD4 count <350 before initiating HAART. • HAART use for at least 2.5 years. • CD4 count increase ≥ 200 cells above pretreatment count. • Consistent increases in CD4 cell count since starting treatment. • HIV viral load consistently below WIHS level of detectability since starting HAART.

Poor CD4 Responders to HAART
	
 • CD4 count <350 before initiating HAART. • HAART use for at least 2.5 years. • CD4 cell increase ≤ 100 cells over pretreatment count. • HIV viral load consistently below WIHS level of detectability since starting HAART.

Off Treatment Progressors
	
 • HIV viral load consistently detectable for at least three years. • Never used HAART or HAART use during pregnancy only.

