
WOMEN'S INTERAGENCY HIV STUDY
 
SECTION 36: MALT/GALT SUBSTUDY PROTOCOL

A. STUDY PURPOSE

The purpose of this study is to evaluate the effects of HIV infection in gut-associated lymphoid tissue (GALT) and endometrial mucosal-associated lymphoid tissue (MALT) in HIV-negative and HIV-positive women at selected stages of HIV disease progression.

Our aims are to compare endometrial, ileal and sigmoid colon tissue samples in selected WIHS participants in order to determine if:

1. The perturbations in GALT, HIV-specific immune responses, apoptosis, and collagen deposition that have been reported in HIV-positive men are also found in HIV-positive women.
2. The patterns of these alterations differ among HIV disease state groups.
3. These alterations are similarly present in endometrial tissue.
4. HIV infection will be associated with reduced numbers of CD4 memory cells, increased lymphocyte activation, apoptosis, cellular turnover, T regulatory cells and collagen deposition in both gut and endometrium; the extent of the abnormalities will be directly correlated with intracellular levels of HIV RNA.
5. The extent of immune abnormality in MALT tissues will be correlated with the extent of HIV disease progression, and with expression of cellular activation markers and level of circulating soluble biologic mediators (in a pattern consistent with inflammation).
6. It is feasible to use endometrial tissue to evaluate overall mucosal lymphoid immunity in future HIV research.

B. BACKGROUND, SIGNIFICANCE, AND PRELIMINARY STUDIES

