nonprogressors (natural controllers) are spared the loss of mucosal T cells and the chronic expression of inflammatory response genes in gut mucosa seen in patients with a more typical HIV course. Since mucosal cells can be easily replaced by cells that traffic in from other sites, depletion of CD4 memory cells within mucosal tissues does not explain the subsequent progression of HIV disease. Chronic immunologic activation and inflammatory responses are closely linked with the long-term outcomes of HIV infection. Lymphocyte activation and changes in blood inflammatory mediators often accompany mucosal abnormalities in both untreated and treated HIV patients. Immune activation is also associated with the extent of CD4 cell recovery after HAART, as well as functional abnormalities. Since activation is not limited to HIV-specific cells, persistent activation is not driven solely by lymphocyte responses to HIV itself. However, repeated episodes of HIV-induced cellular proliferation, differentiation and death may over time lead to increased cellular activation and turnover. Persistent activation could also result from CD4-depleted gut mucosa that permit leakage of bacterial antigens into systemic circulation, a concept that is supported by a recent study by Douek, *et al.*, who found that increased blood bacterial lipopolysaccharide (LPS) levels were associated with HIV infection, increased plasma IFN- γ and frequency of CD38+ HLADR+ CD8 T cells. However, HAART treatment is associated with improvements in systemic immune activation even though mucosal lymphocyte populations remain depleted. Because immune activation is to some extent responsive to HAART, viral replication thus appears to contribute directly to persistent activation, perhaps via stimulation of bystander cells by HIV-triggered responders. Immune activation plays a vital role in maintaining viral replication in mucosal tissues by providing newly susceptible cells, while direct and indirect viral effects result in depletion of susceptible substrate. Pro-inflammatory products of activated cells within the mucosa likely cause injury and apoptosis within the mucosal epithelium.

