1. STUDY POPULATION AND SAMPLE SIZE

A total of 50 WIHS participants, 10 to 15 participants each from five phenotype groups, will be enrolled. Once 15 women from any of the categories have completed the study, that category will be closed to enrollment. The phenotype groups are as follows: (*See Appendix B for complete definitions.*)

- HIV-uninfected women
- Natural controllers
- Good CD4 responders to highly active antiretroviral therapy (HAART)
- Poor CD4 responders to HAART
- Off-treatment progressors

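### Appendix B defines the 'Off Treatment Progressors' by untreated detectable viremia alone, so the group can include women who are not progressing, and both untreated groups bar only HAART

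*Protocol*

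**What the plan says.** Section A of the protocol sets out to study "HIV-positive women at selected stages of HIV disease progression". Aim 5 in the same section states: "The extent of immune abnormality in MALT tissues will be correlated with the extent of HIV disease progression". Inclusion criterion 3 (Section C.3) admits HIV-negative women or "women who meet the criteria for the HIV disease progression groups listed above".

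Section C.1 lists the five phenotype groups and refers the reader onward: "See Appendix B for complete definitions". Appendix B opens with a condition common to all HIV-positive groups: "Women in all categories must have been HIV positive for at least three years, plus". For the Off Treatment Progressors it then adds two items:

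- "HIV viral load consistently detectable for at least three years";
- no HAART ever, or "HAART use during pregnancy only".

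The Natural Controllers carry the same treatment item, paired with viral load consistently below the WIHS level of detectability. The two HAART groups in the same table carry CD4 criteria: a pretreatment count below 350, and a rise of at least 200 (good responders) or at most 100 (poor responders).

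**The concern.** The group's name and the description of the groups promise disease progression, but the criteria deliver only untreated viremia. Detectable virus over three years says nothing by itself about whether a woman's CD4 count fell. If women with stable counts are enrolled, two things follow.

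- **Interpretation.** A tissue difference between this group and another would be reported as an effect of progression when the groups were formed on viremia. Aim 4 already relates abnormality to intracellular HIV RNA, and aim 5 relates it separately to the extent of progression. The group label cannot serve aim 5 without merging the two.
- **Contrast.** To the extent that such women resemble the controllers in their tissue, they would pull the group towards the controllers and shrink that difference.

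The treatment item has a parallel gap. It excludes HAART, not antiretroviral therapy in general. A woman whose virus is undetectable on a non-HAART regimen meets the written definition of a natural controller, and a viremic woman on such a regimen meets the written definition of off treatment. Both groups would then be less purely untreated than their names say.

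**Working it through.** The protocol states no figure on this point, so there is none to reproduce. The main check is a reading of every place that could supply a progression criterion.

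**1. Criteria that apply to each HIV-positive group (Appendix B)**

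| Group | Viral load | Treatment | CD4 or clinical progression |
|---|---|---|---|
| Natural Controllers | consistently undetectable | no HAART outside pregnancy | none |
| Good CD4 responders | undetectable since HAART | HAART for 2.5 years or more | pretreatment <350; rise ≥200; consistent increases |
| Poor CD4 responders | undetectable since HAART | HAART for 2.5 years or more | pretreatment <350; rise ≤100 |
| Off Treatment Progressors | detectable for 3 years or more | no HAART outside pregnancy | none |

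The only item that separates the first row from the last is the viral load. No level above detectability is set.

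**2. Other places**

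- Section C.1 calls Appendix B complete and adds nothing.
- Section C.2.b (Screening Visit) lists a viral load for HIV-positive women and no CD4 count.
- Section C.3 (inclusion) repeats the three years of HIV positivity and refers back to Appendix B.
- Section C.4 (exclusion) has no CD4, progression or antiretroviral item.

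**3. Two test cases against the written rule**

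- Untreated, HIV positive for three years, low but detectable virus throughout, high and stable CD4 count: meets every item and is labelled a progressor.
- HIV positive for three years, on antiretrovirals that are not HAART, virus always undetectable: meets every item and is labelled a natural controller.

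**4. Can a size be given?** It would need the share f of non-progressors in the group, the true difference between progressors and controllers, and the fraction k of that difference that a viremic non-progressor lacks (k = 1 if she resembles a controller fully). The protocol gives none of these, and no alpha, power or SD. The calculation below only shows how much the answer depends on them.

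Assumptions: two-sided alpha 0.05, SD 1, noncentral t, and a true difference of 1.325 SD, chosen because it gives 80% power at 10 per group. Diluted difference = 1.325 × (1 − k·f). For example, f = 0.2 and k = 1 gives 1.325 × 0.8 = 1.06.

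| f | n = 10, k = 1 | n = 10, k = 0.5 | n = 15, k = 1 |
|---|---|---|---|
| 0 | 80% | 80% | 94% |
| 5% | 76% | 78% | 91% |
| 10% | 71% | 76% | 88% |
| 20% | 61% | 71% | 80% |
| 30% | 50% | 66% | 69% |
| 40% | 39% | 61% | 56% |

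Across inputs that the documents do not settle, power runs from nearly unchanged to halved. The table leaves out the added within-group variance of a mixed group, and it concerns only the contrast with the controllers.

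**5. Chance that the group contains at least one non-progressor.** This is 1 − (1 − p)^n, where p is the assumed share in the eligible pool. For p = 5%, 10%, 20% and 30% it is 40%, 65%, 89% and 97% with n = 10, and 54%, 79%, 97% and 99.5% with n = 15. Again p is not in the documents.

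**The case against.** The best defence is that the grouping is coherent on its own terms. The background (Section B.1) says that "nonprogressors (natural controllers) are spared the loss of mucosal T cells", treating non-progression and natural control as the same thing. Untreated viremic women are then the complement, and viremia may be a deliberate proxy for progression. The same section gives viral replication a direct part in persistent activation, so viremia is an exposure of interest in its own right. This stands as a possible explanation of the authors' intent. It does not close the gap: the protocol never states the proxy, and failure to control the virus is not evidence that disease has advanced.

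Several stronger readings are tempting and should not be drawn:

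- *That non-progressors do enter the group.* The rule lets them in; nothing shows how many are in the eligible pool. Since women who start HAART leave the group, those remaining may be selected towards slow progression. That is plausible, but it is inference and unquantified.
- *That the aims order the groups by progression.* Aim 2 asks only whether patterns differ among disease state groups. Aim 5 does not say that the group label measures the extent of progression, and the measure could be settled in an analysis plan that is not shown. The enrolment definition could not be.
- *That the study loses a stated amount of power.* Every input to that claim is assumed, including that viremic non-progressors look like aviremic controllers, which sits badly with the role given to viral replication.
- *That the protocol's own use of the wider term antiretroviral therapy shows an inconsistency.* Section B.2 uses it for recipients in a published study of three women, not as eligibility language.

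On treatment, one can add that the group names say off treatment and natural, and that medications are recorded at screening. Staff might therefore apply the wider meaning, but the written items do not require it.

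**Conclusion.** The concern holds as a defect of definition. As written, the group is untreated viremic women, and women who are not progressing can be included. A difference found in it supports a statement about viremia, not about progression. Likewise, the written rule allows women on non-HAART antiretrovirals into both untreated groups.

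The conclusion rests on the text of Appendix B and on the absence of any further criterion in Sections C.1 to C.4; it needs no numerical assumption. Its size is unknown: the number of women affected, and any loss of power, cannot be stated from the documents. With 10 to 15 women per group, a few misclassified women could matter. The definition acts at enrolment, so it is not a detail that an analysis plan would normally repair. The point merits correction because it changes what the study can conclude, but it does not invalidate the design.

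**What to change.** 1. **Name or criterion.** In Appendix B and Section C.1, rename the group HAART-naive viremic. Alternatively, the investigators add a progression criterion of their own choosing. Renaming costs no recruitment and makes the claim match the definition, though it changes no woman's eligibility. A criterion makes the group fit its present name, but it narrows the pool and also the range of progression that aim 5's correlation needs.
2. **Progression measure.** State in aim 5 that the extent of progression is each woman's CD4 level and slope from existing WIHS data, in place of the group label. The HAART groups already rely on CD4 counts over time, so the cohort should hold them; availability for the untreated women should be confirmed.
3. **Treatment item.** In both untreated groups, extend the classification criterion from HAART to any antiretroviral therapy outside pregnancy. This concerns how women are classified for the study, not how they are treated.

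The cost is wording in Appendix B, Section C.1 and aim 5, and a slightly smaller eligible pool from item 3. The changes do most good before a group fills, because the group closes at 15 completers and the tissue requires colonoscopy and biopsy.
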